1.6 Compliance with Protocol, Good Clinical Practice (GCP)

and Applicable Requirement

This study and all operating procedures will be conducted in accordance with GCP guidelines, protocol and all applicable regulatory requirements issued by US FDA, to protect the rights, safety and well-being of the studying subjects.

1.7 Description of the Population to be Studied

We chose patients with Attention Deficit Hyperactivity Disorder as our subjects in this phase II trial.

2. Trial Objective

The primary objective of this trial was to determine the effective doses and treatment period of PDC-1421 Capsule in subjects with ADHD. The secondary objective was to evaluate the safety of PDC-1421 Capsule in subjects receiving PDC-1421 at various dose levels.

3. Trial Design

3.1 General Design

Table 11. Summary of general design

	Phase II Part II
Design	Double-blind, randomized, parallel group, placebo-controlled
ADHD patients	Stage I: 69 Stage II: 30
Treatment	Randomly assigned on a 1:1:1 basis to one of the three arms: (1) 1 PDC-1421 Capsule plus 1 placebo TID (2) 2 PDC-1421 Capsule TID (3) 2 Placebo TID for 56 days There will be an interim analysis between stage I and stage II.
Assessment interval	Biweekly
Efficacy and safety evaluation	
 • Primary endpoint: efficacy measurement (ADHD-RS-IV) • Secondary endpoints: other efficacy and safety measurements (ADHD-RS-IV, CAARS-S:S, CGI-I, E-SCT, ECG, vital sign, physical examination, hematology, blood chemistry and concomitant medication evaluation)

The Screening phase is intended for diagnosing and assessing the patient for possible inclusion in the study and for providing an adequate washout period. The targeted population of this Part II study is 99 subjects who met the intent-to-treat basis.

[figure not shown]
Part II is a randomized, double-blind, placebo-controlled, parallel-group study.

Stage I: Sixty nine subjects will be randomly assigned on a 1:1:1 basis to one of the three treatment arms (1 PDC-1421 Capsule plus 1 placebo TID, 2 PDC-1421 Capsule TID, 2 placebo TID). Each subject will be treatment for 8 weeks and will return for visit biweekly during the treatment period.

An interim analysis: An interim analysis will be conducted to evaluate the efficacy of PDC-1421 and to decide whether it is necessary enter the second stage of Part II. (See [Section 8](#) for evaluation details.)

Stage II: Thirty subjects will be randomly assigned on a 1:1:1 basis to one of the three treatment arms (1 PDC-1421 Capsule plus 1 placebo TID, 2 PDC-1421 Capsule TID, 2 placebo TID). Each subject will be treatment for 8 weeks and will return for visit biweekly during the treatment period.

Figure 2. General design of procedure

3.2 Primary Endpoint

Improvement of 40% or greater in ADHD Rating Scale-Investigator Rated (ADHD-RS-IV) from baseline up to 8 weeks treatment.

3.3 Secondary Endpoint

Table 12. The secondary efficacy endpoints in part II

Number	Items
1	Symptom remission in ADHD Rating Scale-Investigator Rated (ADHD-RS-IV total score ≤ 18) up to 8 weeks treatment.
2	Change from baseline in the ADHD Rating Scale-Investigator Rated (ADHD-RS-IV), Conners' Adult Attention-Deficit/Hyperactivity Disorder Rating Scale-Self Report: Short Version (CAARS-S:S) and Empirical-Sluggish Cognitive Tempo (E-SCT) score up to 8 weeks treatment.
3	Clinical Global Impression - improvement (CGI -I) score of 2 or lower up to 8 weeks treatment.

3.4 Randomization and Blinding

Table 13. Summary of randomization and blinding

	Phase II Part II
Randomization	Randomized; 1 PDC-1421 Capsule plus 1 placebo TID: 2 PDC-1421 Capsules TID: 2 placebo TID = 1:1:1
Blinding	Double-blind; (1) Unblinding for interim analysis with the required information that predefined for interim statistical analysis (2) Unblinding at the end of trial and share his/her information of randomization if asked by the subject(s) (3) Emergency unblinding at a serious adverse event.

The randomization scheme generated by computer will be prepared by the CRO prior to the start of the study. In the study, subjects will be randomly allocated to the group of one of PDC-1421 Capsule (3 or 6 capsules) or placebo in a ratio of 1:1:1. All subjects and medical staff will be blinded to the treatment assigned till the end of the trial. All

Protocol

emergency unblinding (e.g., due to a serious adverse event) should be reported immediately to the BioLite, Inc. Codes linking randomization number to actual treatment for each subject will be secured in a sealed, opaque envelop and maintained in the study site and research department of BioLite, Inc. The unblinding for interim analysis will be conducted by CRO only.

3.5 Investigational Drug

Investigational drug (PDC-1421 Capsule or placebo) will be maintained and dispensed by study sites. No one but the Investigator and/or his/her designee is permitted to access the investigational drug.

3.5.1 Dosage Form and Strength

PDC-1421 Capsule: 380 mg PDC-1421/capsule

Placebo: 380 mg corn starch/capsule

3.5.2 Manufacturer

ITRI (Industrial Technology Research Institute), Hsinchu county, Taiwan

3.5.3 Route of Administration

Oral administration

3.5.4 Dosing Regimen, packing and labeling

3.5.4.1 Dosing Regimen

Subjects will be assigned with a random number to be allocated into 3 treatment groups on a 1:1:1 basis and treated as following dose regimen:

- **Placebo:** 2 placebo capsules thrice daily for 56 days (8 weeks).
- **Low-Dose:** 1 placebo capsule and 1 PDC-1421 Capsule, thrice daily for 56 days (8 weeks).
- **High-Dose:** 2 PDC-1421 Capsules thrice daily for 56 days (8 weeks).

Dosing regimen for each part of the study is summarized with drug packing on

[Table 14.](#)

3.5.4.2 Packaging

Investigational drug (PDC-1421 Capsule or placebo) are provided by BioLite, Inc. and stored in the sites. Subjects will receive the investigational drug at visit 2 to visit 5 and also be requested to return unused drug at visit 3 to visit 6. Drug packing of the study is summarized with dosing regimen on [Table 14](#).

- **Placebo:** Subjects will receive a drug bag with 42 + 6 (reserve) drug packs at visit 2 to visit 5. Each drug pack contains 2 placebo capsules. Biweekly visits start from visit 2, and will be requested during this 56-day treatment period.
- **Low-Dose:** Subjects will receive a drug bag with 42 + 6 (reserve) drug packs at visit 2 to visit 5. Each drug pack contains 1 placebo capsule and 1 PDC-1421 Capsule. Biweekly visits start from visit 2, and will be requested during this 56-day treatment period.
- **High-Dose:** Subjects will receive a drug bag with 42 + 6 (reserve) drug packs at visit 2 to visit 5. Each drug pack contains 2 PDC-1421 Capsules. Biweekly visits start from visit 2, and will be requested during this 56-day treatment period.

Table 14. Summary of dosing regimen and packaging

Part no.		Part II		
Dosing/Arm		Placebo	Low-Dose	High-Dose
Treatment Duration		56 days	56 days	56 days
Dosing Regimen	Placebo	2 Caps. TID	1 Cap. TID	0
	PDC-1421	0	1 Cap. TID	2 Caps. TID
Packaging		2 Placebo Caps./pack 42 + 6 packs /bag	(1 Placebo Cap. + 1 PDC-1421 Cap.)/pack 42 + 6 packs/bag	2 PDC-1421 Caps./pack 42 + 6 packs/bag
Visit Frequency		Biweekly		
No. of Drug bags Received / Visit		1		

3.5.4.3 Labeling

The drug bag of investigational drug will be clearly labeled as following:

For Part II:

Test Drug: PDC-1421 Capsule/placebo
 Amount: 48 packs (6 reserved packs included; 2 capsules/pack)
 Drug Bag Number:
 Subject Number:
 Visit No.:
 Study Protocol: BLI-1008-002
 Drug Appearance: Brown capsule
 Major Component: Each capsule contains 380 mg of PDC-1421 or placebo
 Dosing: 1 pack (2 capsules) thrice daily after meal for 14 days and with extra 2 day for reserved
 Storage Condition: Store at a dry place at room temperature (15~25°C)
 Lot Number:
 Manufacturer: Industrial Technology Research Institute
 Date of Expiration:
 Sponsor: BioLite, Inc.
 Clinical Sites:
 "Caution: New drug - Limited by Federal Law to investigational use".

試驗藥物: PDC-1421 膠囊/安慰劑
 數量: 48 包小藥包 (含 6 包備用小藥包, 每包小藥包含 2 顆膠囊)
 藥物編號:
 受試者編號:
 回診次別: Visit
 計劃書編號: BLI-1008-002
 藥物外觀: 棕色膠囊
 主成份: 每顆膠囊含有 380 mg PDC-1421 或安慰劑
 劑量: 三餐飯後服用 1 包小藥包(2 顆膠囊), 14 日份 (外加 2 日備用藥)
 儲存條件: 儲存於乾燥常溫之環境 (15~25°C)
 批號:
 製造商: 工業技術研究院
 有效日期:
 廠商: 萊特先進生醫股份有限公司
 試驗機構:
 "Caution: New drug - Limited by Federal Law to investigational use".

注意：試驗新藥僅限特定臨床試驗使用

3.5.5 Study Drug Storage

Investigational drugs will be stored in a locked cabinet at room temperature (15~25 °C) in the study sites.

3.6 Premature Termination or Suspension of the Study

The Investigator and/or the Sponsor may decide to stop the trial if:

- Safety assessment clearly indicates that one study arm is associated with more severe or serious adverse experiences.
- The Sponsor decides to terminate the trial if necessary.

4. Subjects Selection and Withdrawal

Inclusion and exclusion criteria are as follows.

4.1 Inclusion Criteria

1. Aged 18-70 years
2. Female subjects of child-bearing potential must test negative to pregnancy and use appropriate birth control method from the beginning of study to the 15 days later after ending of study
3. Subjects must be able to understand and willing to sign informed consent
4. Able to discontinue the use of any psychotropic medications for the treatment of ADHD symptoms at screening
5. Meet strict operational criteria for adult ADHD according to the Diagnostic and Statistical Manual of Mental Disorders, 5th Edition (DSM-5)
6. A total score of 28 or higher of ADHD Rating Scale-Investigator Rated (ADHD-RS-IV) at screening
7. Have a moderate or severe symptom of ADHD with score of 4 or higher in Clinical Global Impression- Severity (CGI-S) at screening

4.2 Exclusion Criteria

1. Have any clinically significant concurrent medical condition (endocrine, renal, respiratory, cardiovascular, hematological, immunological, cerebrovascular, neurological, anorexia, obesity or malignancy) that has become unstable and may interfere with the interpretation of safety and efficacy evaluations
2. Have any clinically significant abnormal laboratory, vital sign, physical examination, or electrocardiogram (ECG) findings at screening that, in the opinion of the investigator, may interfere with the interpretation of safety or efficacy evaluations
3. Have known serological evidence of human immunodeficiency virus (HIV) antibody
4. Are pregnant as confirmed by a positive pregnancy test at screening
5. Have QTc values >450 msec at screening using Fridericia's QTc formula
6. Have current of bipolar and psychotic disorders

7. Have a current major depression disorder, obsessive-compulsive disorder, post-traumatic stress disorder, generalized anxiety disorder, panic disorder and eating disorder (also if treated but not currently symptomatic)
NOTE: Comorbid diagnoses identified during screening and baseline are acceptable provided that ADHD is the primary diagnosis and the comorbid diagnoses will not confound study data or impair subject's ability to participate (per the Investigator's judgement and documented in source note).
8. Have any history of a significant suicide attempt, or possess a current risk of attempting suicide, in the investigator's opinion, based on clinical interview and responses provided on the Columbia-Suicide Severity Rating Scale (C-SSRS).
9. Have a history of jailing or imprisonment in the past 6 months due to worsening of symptoms of ADHD

4.3 Subject Recruitment and Screening

[figure not shown]
At Visit 1, Investigator will introduce the proposed clinical study to subjects who are interesting in this study. If a subject is willing to undergo an informed consent process based on GCP and participate in this study, the subject will be examined as described in [section 5.2](#). At Visit 2, based on Visit 1 measurements, subject who meets the recruitment criteria will be enrolled in this study.

4.4 Subject Identification

In order to protect each subject's privacy, only subjects' initials will be used as part of subjects' identifications. In addition, a subject number will be assigned to each subject who signed the ICF and each subject who is eligible to enroll in the study.

4.4.1 Subject Initial Allocation

[figure not shown]
A subject's initial will be assigned to each subject by the clinical research coordinator (CRC). Remain blank in the 3rd and 4th space if there have no more initial(s) to be filled in.

4.4.2 Subject Number Allocation

Each subject will be assigned a number by the CRC. All subject numbers will have six digits.

□□-□□□-□□□

The sixth, seventh and eighth digits: the patient number will be consecutive numbers commencing with “001”. At screening visit, these should be blank.

The third, fourth and fifth digits: the screening number will be consecutive numbers commencing with “001”.

The second digit: the site number; UCSF Medical Center will be assigned to “1” and CGMH, Linkou to “2” etc.

The first digit: the part number; Part II will be assigned to “2”.

4.5 Early Withdrawal of Subjects

Subjects will be withdrawn from this trial if they meet one of the following withdrawal criteria:

- Subjects wish to withdraw. (Subjects are not obligated to give reasons for discontinuation from this trial.)
- Subjects can't obey the regulation of the study.

- Investigator(s) consider that withdrawal from study is the best interest of a subject.
- The subject is pregnant during the trial.

Subjects withdrawn from the study due to adverse event(s) must be followed until the events are recovered, recovered with residual effects, death, or lost to follow-up.

5. Treatment of Subjects

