5.2 Treatment Schedule

Potential subjects will be introduced by Investigator or his/her designee of the study design at Screening. If the subject agrees to participate and signs the consent form, the screening process will begin. Suitability of the subject will be evaluated by inclusion/exclusion criteria.

Subjects met eligibility criteria will be assigned with a random number to be allocated into 3 treatment groups on a 1:1:1 basis and treated as following dose regimen:

- **Placebo:** 2 placebo capsules thrice daily for 56 days (8 weeks).
- **Low-Dose:** 1 placebo capsule and 1 PDC-1421 Capsule, thrice daily for 56 days (8 weeks).
- **High-Dose:** 2 PDC-1421 Capsules thrice daily for 56 days (8 weeks).

Subjects will be assessed biweekly (Visit 3, 4, 5, and 6). After the end of study treatment, subjects will be requested to return after two weeks for a follow-up (Visit 7). Screening, safety and efficacy assessments will be performed as [Table 15](#).

During the COVID-19 public health emergency or similar events, the assessments of CAARS-S:S, CGI, ADHD-RS-IV, E-SCT, C-SSRS, AE evaluation, Concomitant Medication, Physical examination and Vital sign can be conducted by telephone, video, or email, but those remote assessments should be documented. All COVID-related changes will be pre-approved by the applicable IRBs.

Table 15. Part II-schedule of assessments

	Screening	Treatment Period					Follow-up
Visit	1	2	3	4	5	6	7
*Week	-2 to 0	0	2	4	6	8	10
Informed consent	√						
Subject information	√						
Medical history	√						
DSM-5	√						
CAARS-S:S	√	√	√	√	√	√	√
CGI- S	√	√					
CGI- I			√	√	√	√	√
ADHD-RS-IV	√	√	√	√	√	√	√
E-SCT	√	√	√	√	√	√	√
C-SSRS	√	√	√	√	√	√	√
Concomitant medication	√	√	√	√	√	√	√
Physical examination	√					√	
Vital sign	√	√	√	√	√	√	√
ECG	√					√	
Laboratory examination							
Pregnancy test	√						√
Hematology	√	√		√		√	
Blood chemistry	√	√		√		√	
Eligibility evaluation	√						
Drug accountability		√	√	√	√	√	
AE/SAE evaluation		√	√	√	√	√	√

*On ±2 days.

**If the interval of visit 1 and visit 2 is within 7 days, Hematology and Blood chemistry test of visit 2 can be skipped.

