5.2.1 Screening Phase (Visit 1)

The Screening phase will be done within 0-2 weeks period and intended for diagnosing and assessing the patient for possible inclusion in the study and for providing an adequate washout period. The items of physical, rating scales and laboratory examination at screening are outlined below:

- Informed consent
- Subject information, including date of birth, gender, race, body height and weight
- Medical history (within six month), including any clinically significant psychiatric, neurological, gastrointestinal, renal, hepatic, cardiovascular, respiratory, metabolic, endocrine, hematological or other major disorders
- Pregnancy test
- Physical examination: skin, head, neck, eyes, ears, nose, throat, heart, lungs, abdomen (liver, spleen), neurological examination, lymph node and extremities.
- Vital sign: heart rate, blood pressure, body temperature
- ECG
- Hematology: RBC, WBC, platelets, hematocrit, hemoglobin, prothrombin time (PT), partial thromboplastin time (aPTT)
- Blood chemistry: AST, ALT, LDH, total bilirubin, BUN, serum creatinine, free thyroxine (FT4), TSH, sodium, calcium, potassium, HbA1c, LDL, HDL, triglyceride, cholesterol
- DSM-5, CAARS-S:S, CGI-S, ADHD-RS-IV, E-SCT, C-SSRS
- Concomitant medication evaluation
- Eligibility evaluation: laboratory data, other tests and evaluation results shall be obtained at Screening to determine the appropriateness of subject enrolled in this study

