5.2.2 Part II.- Treatment Period (Visit 2~6)

Subjects who meet the eligibility criteria will be enrolled and take study drugs. At visits 2 to 5, each subject will be dispensed a supply of study drug sufficient for next 2-week treatment period. The subjects will be instructed to take one dose (i.e., two capsules) after a meal thrice daily. Drug compliance is important for the safety and efficacy evaluations. Study coordinator needs to make sure drug adherence of the subjects is at least

80% during the treatment period. Otherwise, study coordinator(s) must report a protocol deviation including lower than 80% compliance and over 100% compliance during the treatment period. At visits 2, 3, 4, 5 and 6, the safety and efficacy parameters will be evaluated by the following items. Baseline data will be collected before dosing study drug.

- Physical examination: skin, head, neck, eyes, ears, nose, throat, heart, lungs, abdomen (liver, spleen), neurological examination, lymph node and extremities.
- Vital sign: heart rate, blood pressure, body temperature
- ECG (Only at visit 6)
- Hematology: RBC, WBC, platelets, hematocrit, hemoglobin, prothrombin time (PT), partial thromboplastin time (aPTT). (Only at visit 2, 4 and 6)
- Blood chemistry: AST, ALT, LDH, total bilirubin, BUN, serum creatinine, free thyroxine (FT4), TSH, sodium, calcium, potassium, LDL, HDL, triglyceride, cholesterol. (Only at visit 2, 4 and 6)
- CAARS-S:S, CGI- -S (only for Visit 2), CGI- I (only for Visit 3 – 6), ADHD-RS-IV, E-SCT, C-SSRS and concomitant medication evaluation.
- AE/SAE evaluation
- Drug accountability

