5.2.3 Follow-up (Visit 7)

Follow-up visit will be performed at visit 7 after two weeks of the last dose administration. The test items are outlined in the following:

- Pregnancy test
- Vital sign: heart rate, blood pressure, body temperature
- CAARS-S:S, CGI- I, ADHD-RS-IV, E-SCT, C-SSRS and concomitant medication evaluation
- AE/SAE evaluation

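### Pregnancy requires withdrawal, but the test is scheduled only at Visits 1 and 7, so none is set for the first dose or for the 56 dosing days

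*Protocol*

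**What the plan says.** - **Entry.** Inclusion criterion 2 (Protocol 4.1) reads "Female subjects of child-bearing potential must test negative to pregnancy and use appropriate birth control method", with birth control lasting until 15 days after the study ends. Exclusion criterion 4 (4.2) covers women who "Are pregnant as confirmed by a positive pregnancy test at screening".
- **Enrolment.** Protocol 4.3: "At Visit 2, based on Visit 1 measurements, subject who meets the recruitment criteria will be enrolled in this study". Protocol 5.2.1: "The Screening phase will be done within 0-2 weeks period".
- **Withdrawal.** Protocol 4.5 makes withdrawal mandatory when "The subject is pregnant during the trial".
- **Test schedule.** Table 15 marks the pregnancy test at Visits 1 and 7 only. The text agrees: the test is listed in 5.2.1 and 5.2.3 and is absent from the 5.2.2 list for Visits 2 to 6. The flowchart in SAP 5.2.3 has the same two marks, so this is not a table-reading error.
- **Dosing and follow-up.** Protocol 5.2.2: "At visits 2 to 5, each subject will be dispensed a supply of study drug sufficient for next 2-week treatment period". Protocol 5.2.3: "Follow-up visit will be performed at visit 7 after two weeks of the last dose administration".
- **Other laboratory tests.** The footnote to Table 15 says "If the interval of visit 1 and visit 2 is within 7 days, Hematology and Blood chemistry test of visit 2 can be skipped". The implied repeat after a longer gap does not extend to the pregnancy test.

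**The concern.** Unlike the other withdrawal criteria in 4.5, pregnancy can be present without the subject or the site knowing. The schedule has no test during the period when withdrawal would limit exposure: all 56 dosing days lie between the two tests, and the second comes 14 days after dosing has ended. At entry, blood results more than a week old are refreshed at Visit 2, while the result for an absolute exclusion may be two weeks old.

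What is at stake is fetal exposure. Protocol 1.2.4 and 1.4.1 describe single-dose, repeated-dose and genotoxicity studies and mention no reproductive study. The Investigator's Brochure may hold one, but nothing in these documents shows that exposure is harmless.

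**Working it through.** The plan gives no figure of its own to reproduce. The check is day arithmetic plus an expected count.

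**Inputs from the documents.** Visit 2 is day 0, Visit 4 is day 28, dosing ends on day 56 and Visit 7 is day 70 (±2-day windows ignored). Visit 1 falls between day -14 and day 0. There are 23 + 10 subjects per arm (Protocol 8.1), so two active arms give 66 at the maximum, or 46 with Stage I only.

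**Assumptions, not in the documents.** 30-60% of active subjects are women of child-bearing potential. Contraceptive failure is 1-9% per year, before entry as well. A test turns positive L = 10 to 14 days after conception.

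**1. Gap between tests.** At its longest it runs from day -14 to day 70, which is 84 days. Scheduled tests at Visits 2 to 6: 0 of 5.

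**2. Worst-case unnoticed exposure**, for conception on day c:
- Current schedule: 56 - max(c, 0), largest at 56 days for conception at or before the first dose.
- Tests on days 0 and 28: exposure is 0 if c ≤ -L, and 28 days if -L < c ≤ 0. The worst case over all dates is conception just after day 28 - L, which the Visit 4 test misses: 56 - (28 - L) = 28 + L = **38 to 42 days**.

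**3. Expected conceptions during dosing on active drug** = subjects × proportion × 56/365 × failure rate.
- 66 subjects: 66 × 0.30 × 56/365 × 0.01 = 0.03 to 66 × 0.60 × 56/365 × 0.09 = 0.55.
- 46 subjects: 46 × 0.30 × 56/365 × 0.01 = 0.02 to 46 × 0.60 × 56/365 × 0.09 = 0.38.

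**4. What the Visit 2 test adds.** A day -14 test misses conceptions after day -14 - L. A day 0 test still misses those after day -L. The newly detectable window is the difference, (-L) - (-14 - L) = 14 days, whatever L is.
- 66 subjects: 66 × 0.30 × 14/365 × 0.01 = 0.008 to 66 × 0.60 × 14/365 × 0.09 = 0.14.
- 46 subjects: 46 × 0.30 × 14/365 × 0.01 = 0.005 to 46 × 0.60 × 14/365 × 0.09 = 0.10.

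These are upper figures because they take the full 14-day screening interval for every subject. A shorter interval reduces them in proportion.

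**The case against.** The strongest reply is that nothing here is inconsistent. Withdrawal criteria act when a fact becomes known and do not imply a scheduled test. The protocol text, Table 15 and the SAP agree, and neither document sets a testing interval. This stands: a reader might infer a contradiction, but the documents show a design choice that leaves the rule without a scheduled trigger.

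The plan also has protection. Contraception is required, adverse events are reviewed at Visits 2 to 7, and medication is reviewed at every visit. These lower the risk and give biweekly opportunities for self-report. They do not detect an unsuspected pregnancy, and the protocol mentions no test on suspicion.

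Three other readings go too far.
- A Visit 2 test might be credited with all conceptions in the 24 to 28 days before dosing that a day -14 test could miss. With the same detection lag it recovers only 14 of those days.
- One might infer that a pregnancy would go unfollowed. Protocol 7.3 counts findings that cause withdrawal as adverse events, 4.5 follows such withdrawals, and 8.4 lists them with date and reason. Follow-up to outcome is not explicit for pregnancy, but it is partly covered and adds little weight here.
- One might infer that subjects were in fact exposed while pregnant. The documents report no such case.

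Finally, the study was terminated after the interim (SAP 5.4), so a new test can no longer protect its subjects. That also stands.

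**Conclusion.** The point holds as a small safety gap. Under the schedule as written, no test is tied to the first dose and none falls within the 56 dosing days, so a mandatory withdrawal rule depends on someone suspecting pregnancy. Sample size, error rates and efficacy inference are untouched.

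The expected numbers are well below one subject on every assumption tried. They count conceptions, of which fewer would go unnoticed. The range is about 18-fold (2 × 9) because the proportion of child-bearing potential and the failure rate are both assumed. The day counts in step 2 rest on the visit schedule and the assumed detection lag alone. Adding the two tests shortens the worst case without removing it: from 56 to 38-42 days over all conception dates, and to 28 days for conception at or before the first dose. The case for the change is its low burden, not a large expected benefit.

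**What to change.** In Table 15, Protocol 5.2.2 and the SAP flowchart, add for women of child-bearing potential:

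1. A same-day urine pregnancy test at Visit 2, with the result read before the first dose. Urine is the right default because drug is dispensed at that visit, the Visit 2 blood draw may be skipped, and the documents give no same-day laboratory turnaround.
2. A test at Visit 4, by urine or from the blood already drawn there.

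Optionally, add one sentence to 4.5 that any pregnancy is followed to its outcome.

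The cost is a few inexpensive tests at existing visits and two marks in one row of each schedule, with no new visit. It also needs a protocol amendment. Under Protocol 10.2 a change that is not merely logistical or administrative goes to both regulators and the IRBs and must await approval; SAP section 4 lists two regulators and five sites. For the terminated study there is nothing left to change. The edit belongs in any continuation or any later protocol that reuses this schedule.
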